2. LIST OF ABBREVIATIONS AND DEFINITIONS OF TERMS

ADE	adverse device effect
AE	adverse event
ATC	Anatomical Therapeutic Chemical
CFR	Code of Federal Regulations
CI	confidence interval
CIP	clinical investigation plan
CRO	contract research organization
DSMB	data safety monitoring board
eCRF	electronic case report form
FAS	full analysis set
ICF	informed consent form
IWRS	interactive web-response system
IRB	Institutional Review Board
MedDRA	Medical Dictionary for Regulatory Activities
NMC	non-medical complaint
OC	oxidized cellulose
PPS	per-protocol analysis set
SADE	serious adverse device event
SAE	serious adverse event
SAER	serious adverse event report
SI	serious injury
SD	standard deviation
SE	standard error
TBS	target bleeding site
TTH	time to hemostasis
UADE	unanticipated adverse device effect
WHO	World Health Organization

3. INTRODUCTION

This Statistical Analysis Plan is intended to describe the planned statistical analysis of project 3599-001.

In neurosurgery, cerebrospinal fluid (CSF) leaks where disruption of the arachnoid and the dura mater allows CSF to flow to an extradural space, is an event which may lead to severe complications, such as infection, pseudomeningocele, and delayed pneumocephalus. Closure of the dura serves as a mechanical and a biological barrier to both CSF leaks and to the potential entrance of infectious organisms.

To minimize the risk of intra-operative CSF leaks and to potentially reduce post-operative CSF leak rates, different techniques and materials have been used in conjunction to sutures to provide a watertight sealing of the dural incision; one such treatment modality is the use of a fibrin sealant (FS) directly on the suture line to seal the suture holes, as well as the approximated dural edge.

The Investigational Product (IP) for this protocol is FS VH S/D 500 s-apr in its frozen presentation. FS VH S/D 500 s-apr is a 2-component fibrin sealant (FS) made from pooled human plasma. When combined, the 2 components, fibrinogen (human) and thrombin (human), mimic the final stage of the blood coagulation cascade.

In this protocol, FS VH S/D 500 s-apr is intended to be used as an adjunct to sutured dural repair in cranial surgery in patients undergoing elective cranial surgery for the treatment of a pathological condition (eg, benign/malignant tumours, vascular malformations, or Chiari type 1 malformations) specifically located in the PF or ST regions.

4. TRIAL OBJECTIVES

The purpose of this study is to provide data on the safety and efficacy of FS VH S/D 500 s-apr compared to DuraSeal Dural Sealant as an adjunct to sutured dural closure in patients who are undergoing elective cranial surgery for the treatment of a pathological condition (eg, benign/malignant tumors, vascular malformations, or Chiari type 1 malformations) specifically in the PF or ST region.

4.1 Primary Objectives

To evaluate the efficacy of FS VH S/D 500 s-apr compared to DuraSeal Dural Sealant as an adjunct to sutured dural closure.

4.2 Secondary Objectives

To evaluate the safety of FS VH S/D 500 s-apr compared to DuraSeal Dural Sealant as an adjunct to sutured dural closure.

4.3 Exploratory Objectives

Not applicable.

5. STUDY DESIGN AND CONDUCT CONSIDERATIONS

5.1 Study Design

This is a phase 3, prospective, randomized, controlled, single-blind (patient) multicenter study to evaluate the safety and efficacy of FS VH S/D 500 s-apr compared to DuraSeal Dural Sealant as an adjunct to sutured dural closure in a total of 202 evaluable patients undergoing elective cranial surgery for the treatment of a pathological condition (i.e., benign/malignant tumors, vascular malformations, or Chiari type 1 malformations) specifically located in the PF or ST region.

Eligibility according to general and intra-operative criteria will lead to the final selection of the patient into the study, which is determined by the presence of an intra-operative CSF leak after primary dural closure with sutures. Upon detection of CSF leak, the patient's randomization assignment to either IP (FS VH S/D 500 s-apr) or to control (DuraSeal Dural Sealant) stratified by center and surgical regions (PF or ST) will be applied.

5.2 Baseline definition

Baseline values are not applicable for effectiveness measures. Safety measures of clinical laboratory parameters and vital signs will be evaluated with respect to initial values taken during the screening visit.

5.3 Sample Size

The number of subjects in a clinical trial should always be large enough to provide a reliable answer to the questions addressed. This number is usually determined by the primary objective of the trial. If the sample size is determined on some other basis, then this should be made clear and justified. For example, a trial sized on the basis of safety questions or requirements or important secondary objectives may need larger numbers of subjects than a trial sized on the basis of the primary efficacy question (see ICH E1A).

This study is designed to show non-inferiority (NI) of FS VH S/D 500 s-apr compared to DuraSeal Dural Sealant based on the primary composite efficacy endpoint. The

proportion of patients meeting the composite primary endpoint is assumed to be █% for FS VH S/D 500 s-apr and █% for DuraSeal. Using a non-inferiority margin of 10% (the largest clinically acceptable difference), a 1-sided Type 1 error rate (α) of 2.5%, a statistical power ($1-\beta$) of 80%, that one interim analysis is performed after 50% of the patients complete the study, the sample size estimation results in 202 evaluable patients. Assuming a group sequential design utilizing O'Brien-Fleming boundaries, the study may be stopped early for futility if a p-value >0.2486 is observed at the interim. The estimation of sample size was performed using SAS 9.4 software (SAS Institute; Cary, NC). The primary analysis will be performed on the per protocol analysis set (PPS). Assuming that the PPS is 10% less than the total number of randomized subjects, 112 patients per treatment group should be randomized, and there will be 224 patients in total.

5.3.1 Justification of Non-Inferiority Margin

The 10% NI margin is mainly based on literature review, the screening of multiple key opinion leaders (clinical judgment), and a previous clinical study for a comparable product that led to biologic license application (BLA) approval.

- Literature review (Weber 2012)8: In a retrospective analysis of 1395 cranial surgeries, post-operative CSF leaks occur in approximately 7.7%, across all types of cranial surgeries. However, tight dural sutures by inspection were followed by CSF leaks in 4.7%. Tight suturing of the dura mater with additional securing and/or augmentation of the suture by a different technique (covering with muscle or fascia flab, gelitta, fibrin glue, hydrogel gel, or others) is performed 68% of the time. The subgroups with different dural closure augmentation techniques (fleece-bound sealant, glue, dural-plasties, etc.) were too small to detect any statistically demonstrable effect on CSF leaks after cranial surgery.
- Clinical judgment: Based upon discussion with clinicians (neurosurgeons) on the use of dural sealants as an adjunct to suture line, the consensus was that NI could be claimed if the maximum difference of success rate (ie, CSF leakage free) between the new treatment (Tisseel) and the current treatment (DuraSeal) is 10%, with the assumption that the proportion of patients meeting the composite primary endpoint is at least 85.0% for DuraSeal.
- Previous clinical study: A 10% NI margin was used in a previous Phase III pivotal, NI study. In this study, a new dural sealant (Adherus) was compared to the same control (DuraSeal) and the study design including patient population,

eligibility criteria, and the primary endpoint was very similar to the current Tisseel study. Thus, the assumed proportion of [REDACTED] % for DuraSeal in the current Tisseel study is based on results of this previous study evaluating Adherus and DuraSeal.

5.4 Randomization Procedure

Patients will be randomly assigned to FS VH S/D 500 s-apr or DuraSeal Dural Sealant at a ratio of 1:1. Randomization will be stratified by study center and surgical region (PF or ST) with the goal of achieving an approximate 3:1 ratio (ST:PF) of the 2 surgical regions in the randomized study population. Randomization will be controlled via an interactive Webresponse system (IWRS), [REDACTED] using dynamic allocation. On the day of surgery (Day 0), upon confirmation of pre-operative eligibility criteria, a member of the site study staff other than the surgeon will obtain a treatment assignment from the IWRS. Adequate amounts of FS VH S/D 500 s-apr and DuraSeal Dural Sealant will be taken into the operating room for potential use as the study treatment.

Immediately after the patient's intra-operative eligibility for study treatment has been confirmed (ie, spontaneous CSF leak or CSF leak after Valsalva maneuver), the assigned treatment will be revealed to the surgeon and the assigned IP or control will be applied to the CSF leak site. Following surgery, the treatment assignment and the actual treatment applied will be entered in the eCRF for the patient. If the patient's eligibility is not confirmed intra-operatively, the operation will be performed according to hospital standards. The study site designee will document the noncompliant criterion or criteria plus the date and reason(s) for the patient's exclusion in the eCRF, and an entry will be made in the IWRS that the study treatment was not administered.

5.5 Efficacy Assessments

The primary assessment is defined as the proportion of patients who have neither of the following:

- Intra-operative CSF leakage from dural repair after up to two FS VH S/D 500 s-apr/control applications during Valsalva manoeuvre (25 cm H₂O for up to 5 - 10 seconds)
- Post-operative CSF leakage within 30 (+3) days post-operatively.
 - Success is defined as: an intra-operative watertight closure of the dura after suturing during surgery after test with the Valsalva manoeuvre (25 cm H₂O

for up to 5 - 10 seconds) and no CSF leakage within 30 (+3) days post-operatively.

- Failure is defined as: an intra-operative non-watertight closure, which consists of any overt flow, seepage, weeping, or sweating of CSF through the dura suture line, regardless of volume, during surgery or within 30 (+3) days post-operatively.

Secondary efficacy assessments will include:

- Incidence of intra-operative CSF leakage following final Valsalva manoeuvre
- Incidence of CSF leaks within 30 (+3) days post-operatively
- Time in surgery (minutes)
- Time from dural closure (application of IP) until end of surgery
- Length of stay in hospital (days)

All post-operative CSF leaks will be primarily diagnosed based on a detailed history and physical examination including neurological examination. Although not standard of care post-operatively, imaging tests such as computed tomography/magnetic resonance imaging will only be considered if there is a high clinical suspicion of CSF leakage. For example, if CSF leaks externally (eg, incisional leaks, otorrhea, or rhinorrhea), or if there is any bulging suggesting subcutaneous fluid collection at the incision site, needle aspiration and the beta-2 transferrin test will be used to confirm the presence of CSF.

5.6 Safety Assessments

The following secondary safety assessments will be performed during this study:

- Incidence of CSF leaks within 60 (+3) days post-operatively
- Incidence of AEs up to 60 (+3) days post-operatively
- Incidence of SSI according to US NHSN within 30 (+3) days post-operatively
- Number of unplanned interventions within 30 (+3) days post-operatively
- Laboratory values and vital signs (e.g., elevated WBC count, fever [temperature >100.7°F or 38.2°C], tachycardia [pulse >100], hypotension [mean arterial pressure <60]).

Unplanned interventions include meningitis, the management of a deep infection, minimally invasive procedures, and the return to the operating room for neurosurgical complications other than a CSF leak or pseudomeningocele formation, or those related to the subject's pre-existing condition during the 30-day follow-up period following original surgical procedure.

Surgical site infections will be evaluated by the surgeon or designated physician according to CDC/NHSN criteria.

5.7 Completion and Discontinuation

A patient is considered to have completed the study when he/she ceases active participation in the study because the patient has, or is presumed to have, completed all study procedures according with the protocol (with or without protocol deviations). Any other cases are classified as discontinuation.

Reasons for completion/discontinuation will be reported on the Completion/Discontinuation eCRF, including: Completed, AE (eg, death), discontinuation by patient (eg, lost to follow-up [defined as 3 documented unsuccessful attempts to contact the patient], dropout), physician decision (eg, pregnancy, progressive disease, protocol violation[s], recovery), study terminated by sponsor, or other (reason to be specified by the investigator [eg, technical problems]).

Regardless of the reason, all data available for the patient up to the time of completion/discontinuation should be recorded on the appropriate eCRF.

Every effort will be made to have discontinued patients complete the study completion/termination visit. If the completion/termination visit is done as an additional, unscheduled visit, the assessment results shall be recorded with the completion/termination visit. If a patient terminates participation in the study and does not return for the completion/termination visit, his/her last recorded assessments shall remain recorded with his/her last visit. The reason for discontinuation will be recorded and the data collected up to the time of discontinuation will be used in the analysis and included in the clinical study report.

6. STUDY POPULATIONS

6.1 Subject Disposition

The number of subjects who signed informed consent (enrolled), met the pre- and intra-operative inclusion and exclusion criteria (eligible), were randomized, and withdrew early will be displayed for subject disposition. Early withdrawals will be summarized according to reason for withdrawal. Subjects who have been assigned a treatment based on pre-operative criteria, but were found not eligible intraoperatively are not considered to be randomized (for more detail on randomization see section 5.4).

6.2 Analysis Populations

Two types of analyses of effectiveness are planned: analysis of the full analysis set (FAS) and of the per-protocol analysis set (PPS). The primary efficacy analysis will be carried out on the PPS. The analysis using the FAS will be used as a supportive analysis. Assessment of safety will be carried out on all subjects treated (safety analysis set).

- Full analysis set: The FAS will consist of all subjects who were randomized and treated with at least 1 dose of IP/control. Subjects will be analyzed as randomized.
- Per-protocol analysis set: The PPS is defined as a subset of the FAS. Subjects with any major deviation that may impact the primary efficacy parameter will be excluded from the per-protocol analysis set (see section 6.3 for more detail on protocol deviations leading to exclusion).

Safety analysis set: The safety analysis set will consist of all subjects who are treated with IP/Control. Subjects will be analyzed as treated.

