4.3.2 Exclusion Criteria (Intra-operative)

1. Patient has a gap between durotomy edges of >2 mm after primary dural closure in the judgment of the investigator
2. Patients requiring the use of implants made of synthetic materials coming into direct contact with dura
3. Patient has 2 or more separate dural defects
4. Patients with intersecting durotomy scars in the surgical path from a previous operation that cannot be completely removed by the planned dural resection
5. Placement of Gliadel Wafers
6. Major intra-operative complications that require resuscitation or deviation from the planned surgical procedure
7. Patients in whom application of the Valsalva manoeuver is not found appropriate due to increased safety risk
8. Patients requiring the use of other FSs or PEG-based sealants
9. Patients with any other intra-operative findings identified by the surgeon that may preclude the conduct of the study procedure

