5.2 Randomisation

Patients will be randomly assigned to FS VH S/D 500 s-apr or DuraSeal Dural Sealant at a ratio of 1:1. Randomisation will be stratified by study center and surgical region (PF or ST) with the goal of achieving an approximate 3:1 ratio (ST:PF) of the 2 surgical regions in the randomised study population. Randomisation will be controlled via an interactive Web-response system (IWRS), [REDACTED] using dynamic allocation. On the day of surgery (Day 0), upon confirmation of pre-operative eligibility criteria, a member of the site study staff other than the surgeon will obtain a treatment assignment from the IWRS. Adequate amounts of FS VH S/D 500 s-apr and DuraSeal Dural Sealant will be taken into the operating room for potential use as the study treatment.

Immediately after the patient's intra-operative eligibility for study treatment has been confirmed (ie, spontaneous CSF leak or CSF leak after Valsalva manoeuvre), the assigned treatment will be revealed to the surgeon and the assigned IP or control will be applied to the CSF leak site. Following surgery, the treatment assignment and the actual treatment applied will be entered in the eCRF for the patient.

If the patient's eligibility is not confirmed intra-operatively, the operation will be performed according to hospital standards. The study site designee will document the noncompliant criterion or criteria plus the date and reason(s) for the patient's exclusion in the eCRF, and an entry will be made in the IWRS that the study treatment was not administered.

Details of the IWRS and its use will be described in a separate IWRS instruction manual that will be maintained in the trial master file and in each center's investigator trial file.

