5.6 Blinding

This study will be single-blind (patient), as investigator blinding is not possible due to the visual and physical difference between the 2 treatment regimens. Patients will be kept blinded throughout the study. In addition, the surgeon performing the surgery will remain blinded until intra-operative entry criteria have been confirmed (see Section 5.2).

Otherwise, investigators, surgery personnel, site study personnel, clinical research organisation personnel, and sponsor personnel will not be blinded. Adequate block size will be used to prevent guessing the allocation in the trial and to ensure real blinding. Flexible random block sizes will be also used based on the stratification factors (site and surgical region), eg, relative small block sizes will be used to maintain balance in small strata whereas relative large block sizes will be used in large strata.

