9.3 Analysis Populations

9.3.1 Full Analysis Set (FAS)

The patients who were randomised and treated with at least 1 dose of IP/control will be included in the Full Analysis Set (FAS).

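### The full analysis set requires a dose, so a patient left untreated after the surgeon has seen the arm drops out of both efficacy sets

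*SAP*

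**What the plan says.** SAP 6.2 gives the FAS rule: "The FAS will consist of all subjects who were randomized and treated with at least 1 dose of IP/control". FAS patients are analysed as randomised. Protocol 9.3.1 sets the same two conditions, randomised and treated. SAP 6.2 makes the PPS a subset of the FAS, makes it the primary efficacy set and calls the FAS supportive. No third efficacy set is planned.

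The order of events is in Protocol 5.2, 7.3 and 7.4 and SAP 5.4. A staff member other than the surgeon obtains the assignment on the day of surgery, before the operation. Intra-operative criteria and the leak are then checked. Once eligibility is confirmed, "the assigned treatment will be revealed to the surgeon and the assigned IP or control will be applied to the CSF leak site". Protocol 5.6 adds that "the surgeon performing the surgery will remain blinded until intra-operative entry criteria have been confirmed".

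SAP 6.1 deals with patients who were assigned an arm "but were found not eligible intraoperatively are not considered to be randomized". SAP 7.2 analyses only patients with endpoint data and replaces no missing values.

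**The concern.** A condition that the patient must have been treated does no harm when the decision to treat cannot depend on the arm. Here the decision is carried out after the surgeon knows the arm. The two products are also prepared and applied differently (Protocol 6.9.1 and 6.9.2), so a practical reason for not applying one need not apply to the other. No bad faith is required.

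A patient lost at this step is lost from the FAS and the PPS together. The FAS is the only check on a per-protocol primary analysis. If both sets have lost the same patients, their agreement says nothing about this source of bias. SAP 13.2 plans a listing of patients excluded from the PPS, but the SAP names no table or listing of randomised patients who fall outside the FAS.

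**Working it through.** **Who is in which set.** Applying the definitions to four kinds of patient:

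| Patient | Randomised (SAP 6.1) | FAS | PPS |
|---|---|---|---|
| Found ineligible during surgery, before the reveal | no | no | no |
| Revealed, other study product applied | yes | yes, as randomised | no |
| Revealed, one application, still leaks | yes | yes, as a failure | yes, if no major deviation |
| Revealed, nothing applied | yes | **no** | **no** |

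Only the last row is a gap. That patient is randomised on the SAP's own terms and is removed by an event that follows the reveal.

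**Planned size.** The definition has no figure of its own. The 112 per arm used below is the plan's figure: 202 / 0.9 = 224.4, stated as 224, or 112 per arm (Protocol 9.2, SAP 5.3).

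**Inputs to the illustration.**
- Margin of 10 points and two-sided 95% interval: SAP 10.1.
- Control rate: Protocol 9.2.1 gives 90.6%, and 0.906 × 112 = 101.5. I use 101/112 = 90.2%.
- Test rate: redacted. I assume treated test patients succeed at about the control rate.
- Number m of revealed-but-untreated test patients: not in the documents. I vary it.

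**Formula.** d = p_T − p_C; SE = √[p_T(1−p_T)/n_T + p_C(1−p_C)/n_C]; lower limit = d − 1.96 × SE. This is unadjusted. SAP 10.1 uses a covariate-adjusted logistic model with a delta-method standard error, so the limits are approximate.

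**Worked case, m = 3.**
- FAS as written: p_T = 98/109 = 0.8991, d = −0.0027, SE = 0.0403, limit = −0.0027 − 0.0790 = −8.2%.
- All 112 counted, untreated as failures: p_T = 98/112 = 0.8750, d = −0.0268, SE = 0.0420, limit = −0.0268 − 0.0824 = −10.9%.

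| m, test arm only | Treated successes | Lower limit, FAS as written | Lower limit, untreated counted as failures |
|---|---|---|---|
| 0 | 101/112 | −7.8% | −7.8% |
| 1 | 100/111 | −7.9% | −8.8% |
| 2 | 99/110 | −8.0% | −9.9% |
| 3 | 98/109 | −8.2% | −10.9% |
| 5 | 96/107 | −8.4% | −13.0% |

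**Range for three patients.**
- All three counted as successes: 101/112 against 101/112, limit −7.8%.
- Three untreated in each arm, all counted as failures: 98/112 against 98/112, SE = 0.0442, limit −8.7%, against −8.0% as written (98/109 in each arm).
- Three in the control arm only, counted as failures: d = 101/112 − 98/112 = +0.0268, limit −5.6%, against −7.6% as written.

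What matters is an imbalance between arms in patients who would have done badly. The table shows how far the supportive result depends on a handful of patients; it does not estimate a bias.

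**The case against.** The strongest objection concerns the mechanism. A reader might infer that the surgeon, having seen the arm, can invoke intra-operative exclusion 8 (another sealant needed) or 9 ("Patients with any other intra-operative findings identified by the surgeon that may preclude the conduct of the study procedure"), and that SAP 6.1 then treats the patient as never randomised. The documents do not support this. Protocol 5.6, 7.3 and 7.4 place all intra-operative criteria before the reveal, while the surgeon is blinded. Protocol 5.7.2 allows other fibrin or PEG-based sealants only as rescue when the assigned treatment fails, and treats a breach after randomisation as a protocol violation. Followed as written, SAP 6.1 covers only patients found ineligible before the reveal, and leaving those out is defensible.

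Nor do hard leaks generally escape the FAS. One application is enough for entry, and a leak that persists afterwards counts as a failure. To lose a patient, even the first application must be withheld.

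It is also fair to say that application should follow the reveal at once, that the FAS is only supportive, and that a shortfall between the randomised count and the FAS denominator could be noticed in the disposition table.

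These points narrow the concern without removing it. No section requires the eligibility decision to be recorded before the reveal, and SAP 6.1 states no cut-off at that moment. A patient who is eligible, revealed and untreated still falls outside both efficacy sets, and no report of such patients with reasons is planned.

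**Conclusion.** The concern holds as a gap in the FAS definition: the dose condition acts after the surgeon knows the arm, and the PPS inherits the loss. It is not evidence that patients will be removed selectively. The number affected may be small or zero.

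Under the stated assumptions, the supportive conclusion survives one or two untreated test-arm patients counted as failures (limits −8.8% and −9.9%) and is lost with three (−10.9%, against −8.2% under the current definition). This rests on an assumed count, an assumed test rate, all such patients being in the test arm, and all being counted as failures. The non-inferiority decision itself rests on the PPS and is not changed by redefining the FAS. This is an inexpensive improvement to the supportive analysis that should be made.

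**What to change.** - **Protocol 9.3.1 and SAP 6.2:** define the FAS as all patients with confirmed intra-operative eligibility, including the confirmed leak, whose arm was revealed to the surgeon, treated or not, analysed as randomised.
- **SAP 6.1:** state that a patient is regarded as not randomised only if ineligibility was recorded before the reveal.
- **SAP 7.2:** add an exception that counts revealed-but-untreated patients as failures in the supportive FAS analysis. Without it the new definition could change nothing, because the endpoint is leakage after up to two applications and patients without endpoint data are dropped. Protocol 9.4 permits imputation where it is specified.
- **SAP 13:** report revealed-but-untreated patients by arm, with reasons. This is needed alongside the scoring rule, because failures counted in the control arm would favour the test product.

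Keep the PPS as primary and the safety set as treated. The planned 224 is unaffected. The cost is a few sentences, possibly a few more patients to follow and count, and a FAS result that may be slightly less favourable.
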